1. ABSTRACT

Background: In the U.S., increased intake of fast food and highly processed foods (a “Western-style” diet) has been coincident with the dramatic rise in asthma. Observational studies demonstrate a link between a dietary pattern and asthma morbidity at the level of the individual, and limited trials of counselling for a healthier diet have shown promise in improving asthma health.

Objectives: The objective of the study is to demonstrate the feasibility of a randomized, controlled trial of complete dietary replacement (feeding study) in a population of adults with asthma, and to provide measures of variability in the proposed outcomes (symptoms, lung function, markers of inflammation and oxidative stress) to inform sample size calculation for a larger, definitive trial.

Methods: The study is a feasibility trial of a prudent (high in fruit and vegetables, whole grains, low-fat dairy) versus Western-style (high in processed foods, fast food, sweets) diet intervention in adults with asthma. Eight to twelve adult women (ages 18-55) who meet eligibility criteria will be enrolled. At baseline, demographic information, asthma symptom scores, usual dietary intake, anthropometric measures and DEXA, spirometry, FENO, blood, urine, nasal, and sputum samples will be collected. Participants will then be randomized to either the Western-style diet or a prudent diet. Prior to initiating the diet, they will have assessment of select biologic outcomes (FENO, spirometry, symptom assessment, biomarkers of oxidative stress and inflammation in urine and serum, and nasal swab). After 6 days of the randomized diet, they will repeat these assessments and undergo induced sputum for local (pulmonary) biomarkers of inflammation and oxidative stress. The participants will then have a 4-8 week washout period, and repeat the same order of assessments prior to and after receiving the alternate diet assignment. During each of the 6-day interventions, participants will record asthma-related symptoms via a standardized questionnaire. At the final session, participants will provide feedback on the acceptability and palatability of the dietary interventions and assessments. As this is a feasibility study, we will use results to assess the process and procedures necessary to scale the intervention to a larger study population.

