2. OBJECTIVES

The primary objective for this study is to determine the feasibility of a randomized, crossover trial of a Western-style compared to a prudent dietary intervention among Baltimore City adults with asthma. Our secondary objective is to gather preliminary data on markers of systemic and airway inflammation and oxidative stress, lung function, and changes in the microbiome induced by diet to inform sample size for a definitive trial.

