- 11) **Urine collection:** Prior to enrollment, all participants will submit a urine sample for pregnancy testing, and urine will also be collected for analysis at each assessment visit. Urine biomarkers, including LTE4 and F-isoprostane, will be measured to assess oxidative stress and inflammation. We will also measure other markers of inflammation/chemical exposure that may affect asthma control. Any excess urine will be stored for future analyses.
- 12) **Nasal swab collection:** Nasal swab (and optionally, oropharyngeal and skin swab) collection will occur at each assessment visit, before and after each dietary intervention, to obtain a sample for cellular examination. Analysis of biomarkers in nasal specimens will include (1) cell count and differential, (2) cytokines, (3) chemokines, and other markers of inflammation, (4) microbial assessment.

Randomization: Randomization will occur within approximately one to two weeks of enrollment. Participants will be randomized using a computerized random assignment table with permuted blocks. Participants will be aware of their assignment as the study cannot be blinded.

iii. Intervention

Participants will be provided with all meals for 6 days through the Nutrition Core at the ICTR. Meals will be calorically balanced such that the “prudent” versus “Western-style” intervention will contain similar caloric counts.

Participants will be instructed not to consume meals or snacks outside of those provided and will be asked to visit the research clinic at most twice to pick up their meals: once at initial assessment, and mid-way through the intervention period, they may either return to the clinic to pick up the remainder of their meals or their meals will be delivered to their home. For each day of this controlled feeding, participants will also complete a **daily diary**. The daily diary asks about study foods not eaten, non-study foods eaten, and beverages consumed over the past day. Participants will also report **daily symptom assessment** with validated symptom scales and rescue inhaler use daily during the 6-day dietary intervention, as well as exposures that may affect asthma control.

A washout period of approximately 4-8 weeks separates each intervention period; the washout period allows ad libitum food intake.

Description of Diets:

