- 8) **Sputum induction:** Participants will be instructed through an induced sputum procedure via hypertonic saline nebulization. Sputum inductions and processing will be performed following published protocols. Briefly, after baseline spirometry, an ultrasonic nebulizer will be used to deliver hypertonic saline for at most a total of 20 minutes. The subject will be asked to expectorate sputum into a specimen cup placed on ice. Lung function will be monitored to ensure participant safety. If there is a fall in FEV₁ of $\geq 20\%$ compared baseline FEV₁ prior to sputum induction at any point or if the patient is unwilling or unable to continue, sputum induction will be terminated and albuterol administered as needed.
- 9) **Feedback session:** We will solicit feedback on acceptability of intervention and satisfaction with study structure, including study instruments administered to optimize participant experience and retention for an anticipated, larger-scale trial.

b. Study duration and number of study visits required of research participants

Each study participant will be enrolled for a maximum of approximately 16 weeks, and with rolling enrollment we anticipate completion of all study visits within 1 year. Each research participant will be required to attend a baseline clinic visit and four assessment clinic visits. In addition, during each of the Western and prudent intervention periods, the participants will be required to pick up their meals at most twice: once at initial assessment, and mid-way through the intervention period, they

may either return to the clinic to pick up the remainder of their meals or their meals will be delivered to their home. In total, each research participant will be required to make five to seven study-related visits.

c. Blinding, including justification for blinding or not blinding the trial, if applicable.

It is not possible to blind participants to this protocol, as they will be aware which diet they have been assigned. Participants will be randomized using a computerized random assignment table with permuted blocks to receive either the “Western” or “prudent” diet first, and they will receive the alternate diet after the washout period. We will blind investigators and all study staff outside of the nutrition CRU staff to diet assignment.

d. Justification of why participants will not receive routine care or will have current therapy stopped.

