Analysis Plan: Participant feedback will be analyzed via a deductive approach for content analysis. We will examine for themes within the interview data which either support the current approach or suggest that procedure modification could improve feasibility and participant experience in a future trial. The distributions of all quantitative variables will be examined for outliers and missing data points. Next, the distributions of serum lipids, carotenoids, fatty acids, FEV₁, FeNO, and sputum neutrophil % will be summarized and displayed for each time point. Post-challenge levels of these outcome variables will be compared between prudent and Western diet interventions using paired t-tests, displaying the calculated differences as percentages and absolute differences. Group 1 will be defined as the group randomized first to the Western diet, and Group 2 will be defined as the group randomized first to the prudent diet. We will also evaluate for evidence of carryover effect (measurable effect from order of intervention), although the washout period has been carefully selected to prevent this. We will examine differences in the outcome variables by order of intervention occurrence and apply the t-test. If the outcomes do not appear normally distributed, we

will transform them so that they meet assumptions of normality. In addition, we will calculate the intraclass correlation coefficient (ICC) using mixed effects models to assess the temporal variability of target biomarkers. The ICC is a measure of reproducibility and commonly used to assess the suitability of biomarkers to properly characterize exposures.

Power Calculations: Power calculations cannot be completed for the primary, qualitative outcome of feasibility.

Sample Size: We propose a small study as a feasibility trial to generate preliminary data for a future, larger intervention that will be powered to detect clinical endpoints.

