Study Duration: The duration of intervention, 6 days, is shorter than most other diet intervention studies to date. Our prior intervention was of one-month duration, with outcomes similar at two weeks and one month. Other trials of diet intervention in asthma have also been at least two weeks in duration, though this duration of meal replacement is costly and difficult to scale. Importantly, just four hours after a high-fat diet challenge, meaningful changes in lung function and inflammatory markers have been detected, suggesting the presence of short-term effects on asthma health. We intend to further evaluate these short-term effects, both a novel and important aspect of the proposal that will inform duration and timing of outcome assessment in the planned, future trial. Based on variability of the secondary outcomes assessed in this trial and degree and directionality of change seen, we anticipate that this pilot will inform both feasibility as well as necessary duration of a future, definitive trial.

As this is a pilot study, we do not intend to complete interim analyses.

d. Early stopping rules

As this is a pilot study, there will be no formal criteria for stopping the study early, however participants may choose to leave the study early or may leave the study early at the determination of the Principal Investigator.

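### The diets are compared by paired t-tests with no period term; a period effect, if there is one, would inflate the SD of the paired differences and, with unequal completed sequences, bias the diet difference

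*Combined protocol and SAP*

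**What the plan says.** The design is a two-period, two-sequence crossover in 8 to 12 women. Section 2 gives the primary objective as "to determine the feasibility of a randomized, crossover trial of a Western-style compared to a prudent dietary intervention". Section 4.a.iii separates the diets: "A washout period of approximately 4-8 weeks separates each intervention period".

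The diet comparison is in Section 7.c, Analysis Plan: "Post-challenge levels of these outcome variables will be compared between prudent and Western diet interventions using paired t-tests". The same paragraph defines Group 1 (Western first) and Group 2 (prudent first) and adds an order check: "We will also evaluate for evidence of carryover effect (measurable effect from order of intervention"; "We will examine differences in the outcome variables by order of intervention occurrence and apply the t-test". It does not say what follows if that test is positive. Mixed models are named only for the intraclass correlation. No section adds a period term to the diet comparison.

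The variability results have a stated use. With a later trial in view, the abstract's objectives include "to provide measures of variability in the proposed outcomes (symptoms, lung function, markers of inflammation and oxidative stress) to inform sample size calculation". Section 7.c (Study Duration) looks ahead to that trial "Based on variability of the secondary outcomes assessed in this trial and degree and directionality of change seen". The plan does not say which SD will be carried forward.

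**The concern.** In a crossover, anything that shifts outcomes between the first and second period, such as season, familiarity with the procedures or drift in asthma control, pushes the within-person diet difference one way in Group 1 and the other way in Group 2. A paired t-test pools the two groups, so the shift is counted as random scatter. If the groups finish with different numbers, part of it also enters the mean.

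At stake is mainly the SD. The SD of within-person differences is the natural input for sizing a crossover, and this pilot exists partly to supply variability estimates. The diet estimate matters less, but its direction is meant to guide the next trial too.

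**Working it through.** The plan states no effect size, SD, alpha or power for these outcomes, so there is no figure of its own to reproduce.

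**Inputs from the documents.** 8 to 12 participants (abstract; Section 4.a.i); permuted blocks with block size and ratio not given (Sections 4.a.ii and 4.c); early withdrawal possible, no rate given (Section 7.d).

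**Assumed inputs.** Between-person SD = 1; between-period correlation ρ = 0.6 (range 0.4 to 0.8); period effect P = 0.25 or 0.5 SD; definitive crossover sized for a 0.5 SD diet difference, two-sided 5%, 80% power.

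**Notation.** d = Western minus prudent within a participant, τ = diet effect, P = period 1 minus period 2, n1 and n2 = completers in Groups 1 and 2, n = n1 + n2. Without carryover, E(d) = τ + P in Group 1 and τ − P in Group 2.

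**1. SD of paired differences.** Expected variance = 2(1 − ρ) + P² × 4·n1·n2/[n(n − 1)]. At 6/6 the multiplier is 144/132 = 1.091.
- P = 0: 0.800, SD 0.894.
- P = 0.25: 0.800 + 0.068 = 0.868, SD 0.932, ratio 1.042.
- P = 0.5: 0.800 + 0.273 = 1.073, SD 1.036, ratio 1.158.

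**2. Size of the next crossover** (noncentral t, n − 2 df).

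| ρ | SD ratio, P 0.25 / 0.5 | N, P 0 / 0.25 / 0.5 |
|---|---|---|
| 0.4 | 1.028 / 1.108 | 40 / 42 / 49 |
| 0.6 | 1.042 / 1.158 | 28 / 30 / 36 |
| 0.8 | 1.082 / 1.297 | 15 / 17 / 24 |

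**3. Bias of the paired mean** = P(n1 − n2)/n.
- 6/4: 0.25 × 2/10 = 0.05; 0.5 × 2/10 = 0.10.
- 5/3: 0.25 × 2/8 = 0.06; 0.5 × 2/8 = 0.13.
- Equal sequences: zero.

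**4. Coverage of the paired 95% CI** (simulation, 200,000 trials per setting, ρ = 0.6; P = 0 / 0.25 / 0.5).
- 6/6: 95.0 / 95.7 / 97.4%.
- 4/4: 94.9 / 95.7 / 97.3%.
- 6/4: 95.0 / 95.4 / 96.5%.
- 5/3: 95.0 / 95.3 / 96.3%.

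Only a stronger imbalance reverses this: at 8/4 with P = 0.5, coverage is 94.5%.

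**5. Sampling error of the SD.** The chi-square 95% limits are 0.70 to 1.75 times the estimate with 10 df (n = 12) and 0.64 to 2.20 times with 6 df (n = 8). Both ranges are much wider than a 4% or 16% inflation.

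**6. Price of the period term when P = 0** (ratio of critical t, times ratio of standard errors).
- 6/6: 2.228/2.201 = 1.012.
- 4/4: 2.447/2.365 = 1.035.
- 6/4: (2.306/2.262) × √(0.0833/0.0800) = 1.040.
- 5/3: (2.447/2.365) × √(0.1067/0.1000) = 1.069.

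**7. RMSE with unequal sequences.** Paired: √[0.8/n + bias²]. Adjusted: √[0.2(1/n1 + 1/n2)].
- 6/4: paired 0.287 (P 0.25) and 0.300 (P 0.5); adjusted 0.289; equal at P = 0.29.
- 5/3: paired 0.322 and 0.340; adjusted 0.327; equal at P = 0.33.

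**8. What the order test measures.** Suppose the first diet leaves carryover L_W (Western) or L_P (prudent) in period 2. Then E(d) = τ + P − L_W in Group 1 and τ − P + L_P in Group 2. The difference between groups is 2P − (L_W + L_P). Applied to within-person diet differences, the test responds to period and average carryover together and cannot separate them.

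**The case against.** The strongest reply is that no period effect has been shown and several features make one less likely. Enrolment is staggered ("with rolling enrollment we anticipate completion of all study visits within 1 year"), usual asthma care continues (Section 4.d), and spirometry and sputum induction are first done at screening, which takes up some of the learning effect. Most outcomes are also measured before each diet, so drift between periods can be inspected descriptively, though sputum is not collected at those visits. All of this stands. It lowers the likelihood of harm but does not exclude it.

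A second reply is that the plan already tests for an order effect. It does, but the result adjusts neither the diet estimate nor the SD.

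A third is that the paired t-test can be the better choice. For small period effects it is: with unequal sequences its RMSE is slightly lower until the period effect reaches about 0.3 SD. That is a fair reason to keep it as a sensitivity analysis.

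The link to sample size is partly inferred. The plan does not commit to the paired-difference SD, and it does not fix the definitive trial as a crossover.

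A reader might go further and call the order test a period test that has nothing to do with carryover. The documents do not support that. On within-person differences it reflects both (step 8), and the plan's wording could equally mean comparing outcome levels or totals between the groups, which is the usual carryover test.

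**Conclusion.** The point holds as an optional improvement. The diet comparison has no period term, and this matters only if a period effect exists. Under the assumed inputs at 6/6 and correlation 0.6, the SD of paired differences is inflated by 4% or 16%, and a later crossover grows from 28 to 30 or 36. With unequal completers the bias is 0.05 or 0.10 SD at 6/4 and 0.06 or 0.13 SD at 5/3.

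Two stronger inferences are not supported. The first is that the paired t-test is invalid: with no period effect it is valid and slightly more precise, and with one its intervals are at or above nominal coverage in the layouts the plan makes plausible. An 8/4 split would need an allocation that the plan does not state. The second is that the next trial would be underpowered: an inflated SD makes it larger. The inflation is also smaller than the sampling error of an SD from 8 to 12 women, and the primary outcome, qualitative feasibility, is unaffected.

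The period effect, the correlation and the dropout pattern are all assumptions; the documents give none of them.

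**What to change.** In Section 7.c, keep the planned display of percentage and absolute differences and replace the paired t-test sentence with wording such as:

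*Post-diet values will be compared between diets with a model including diet and period as fixed effects and participant as a random effect (for completers, the two-sample analysis of within-person diet differences by Group 1 and Group 2). The diet difference will be reported with its 95% CI. The SD carried forward to size a definitive crossover will be the pooled within-sequence SD of the within-person differences, with its 95% CI. The paired t-test will be a sensitivity analysis.*

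State what the order t-test is applied to. If it is applied to within-person diet differences, describe it as a test of period and/or average carryover, which it cannot separate.

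The change needs no new data or visits. It costs one degree of freedom. With no period effect the CI is about 1% wider at 6/6 and about 7% wider at 5/3, and with unequal sequences RMSE is slightly higher when the period effect is below about 0.3 SD.

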8. RISKS

- a. Medical risks, listing all procedures, their major and minor risks and expected frequency, and**
- b. Steps taken to minimize the risks.**

Urine collection: Urine collection is considered a very low risk procedure. Urine will be collected the morning of the in-person screening visit and the morning of each of the four assessment visits.

Questionnaires: The only risk involved in completing the questionnaires is the potential for breach of confidentiality. Unique identifiers will be assigned to participants and these will be used to label all paperwork, including questionnaires. Some participants may also feel uncomfortable answering personal questions, but all participants will be offered the opportunity to refrain from answering any questions they do not want to answer. Participants will answer questionnaires/logs at the baseline visit, and during each of the intervention periods.

Dual Energy X-ray Absorptiometry (DEXA) scan: The DEXA scan is considered a safe test and is widely used in clinical practice for estimation of bone mineral density in screening for osteoporosis, and it is also widely used in research studies including the National Health and Nutrition Examination Survey as conducted by the Centers for Disease Control and Prevention. The risks of this scan are directly related to the radiation dose received by the participant. We estimate that the dose of radiation received during a DEXA total body scan is around 0.001 rem per DEXA scan, a minuscule dose compared to the dose of 0.04 rem for an abdominal x-ray (Huda, 1996). Women capable of bearing children will receive a urine pregnancy test prior to the DEXA scan to exclude pregnant women from this procedure. The DEXA scan will only be performed once per participant, at the baseline visit.

Spirometry: Spirometry is a routine clinical procedure that entails little risk. One minor risk is the slight discomfort of forceful exhalation, but this will be minimized by effective coaching and administration by trained study personnel. Spirometry will be performed at the baseline visit and during each of the four assessment visits.

The drug albuterol will be administered during spirometry and can lead to tremor, nervousness, tachycardia, palpitations, and headache. These reactions are transient and rare (< 5%) with the proposed doses used for this study, and if they occur, we will monitor the patient until they return to baseline. High dose albuterol may cause arrhythmias and hypokalemia. However, these reactions are very unlikely with the doses used for this study.

Induced sputum: Hypertonic saline nebulization can cause bronchospasm; to prevent this, albuterol will be administered prior to the procedure, hypertonic saline will be administered in escalating doses, and lung function will be measured throughout the protocol to prevent excessive responses. If there is a fall in post-bronchodilator FEV₁ of $\geq 20\%$ compared to FEV₁ prior to sputum induction at any point or if the patient is unwilling or unable to continue, sputum induction will be terminated and albuterol administered as needed. Sputum induction will not be performed or will be terminated in subjects with post-bronchodilator FEV₁ < 60% predicted. Risks are minimized by conducting the test in a medically supervised environment with trained personnel, and a physician will be available in the clinic during the procedure. Oxygen and albuterol via metered dose inhaler will be available and additional therapy will be administered as deemed appropriate depending on the circumstance. In the event of an emergency, the JHH Adult Code team will be called to respond. Induced sputum will be conducted at the baseline visit and during each of the two assessment visits following each dietary intervention.

Stool/fecal strip collection: Stool/fecal strip collection is considered a very low risk procedure. Samples will be collected during each of the four assessment visits.

FeNO measurement: FeNO measurement is considered a very low risk procedure. Measurement of exhaled nitric oxide will be obtained according to ATS guidelines at each of the four assessment visits.

Serum collection via venipuncture: Phlebotomy is a routine clinical procedure. There is a risk of minor discomfort or bruising at the site of the blood draw. In addition, some people experience lightheadedness. Very rarely, an infection can develop at the venipuncture site. In order to reduce

risks, a trained staff member who is experienced in phlebotomy will perform the venipuncture. Phlebotomy will be performed at each of the four assessment visits.

Nasal swab collection: The main risk of cell sampling is minor discomfort while the sample is being collected, though the discomfort should subside immediately after the sample is taken. There is a slight risk of some nasal bleeding during or just after the sample is collected, and rarely, an infection may occur at the sampling site. In order to minimize these risks, a staff member who is experienced and trained in nasal sample collection will perform the procedure. Nasal swab collection will be performed at each of the four assessment visits.

Dietary intervention: The two periods of dietary interventions pose minimal risk. Participants may experience some bloating and other minor gastrointestinal (GI) discomforts related to the high fruit, dairy, and fiber content of the intervention diets. Our experience suggests that GI discomfort is generally minor and subsides quickly, and GI problems often resolve soon after changes in diet. Participants are monitored for reactions to the diets and, if necessary, the diet can be modified or terminated.

c. Plan for reporting unanticipated problems or study deviations

Any serious or unexpected adverse event will be reported to the IRB according to institutional reporting requirements; other adverse events will be reported to the IRB at the time of continuing review. Protocol deviations will be reported to the IRB according to institutional reporting requirements: minor or administrative deviations to the protocol will be reported with the continuing review; major, non-emergent deviations will be submitted for review; and emergent deviations will be reported as soon as possible and at least within 5 days to the IRB.

d. Legal risks such as the risks that would be associated with breach of confidentiality

The risk of breach of confidentiality will be minimized by using unique identifiers for participants and keeping the record that links the identifier to the participant in a locked file cabinet or office and/or password protected database accessible only to the investigators and study staff.

e. Financial risks to the participants.

In the rare event that a participant has a reaction to diet intervention and he/she seeks medical care, he/she will be responsible for payment of those services. The subject will not be charged for any of the proposed procedures and will be compensated for time spent in the study.

